Re-ulceration, re-infection, re-amputation and hospital re-admission after partial foot amputation for digital gangrene is well documented in the literature in both diabetic and PAD cohorts(6). Across the literature, rates of re-amputation at five years post-index surgery for diabetic foot complications range from 45-65% (6, 7). A recent study by Collins et al reported that, out of 146 Irish patients undergoing minor amputations, 43% (n=63) required further ipsilateral amputation, 21 (14.4%) of which were trans-tibial or trans-femoral(8). Chronic kidney disease, diabetes with or without poor glycaemic control, peripheral neuropathy, peripheral arterial disease, ongoing tobacco smoking, obesity (BMI >30), concurrent sepsis at the time of index operation have all been identified as independent risk factors for amputation failure and the need for revision(9-11). While numerous studies have investigated patient-dependent factors predictive of amputation failure, there is a dearth of evidence examining the impact of surgical technique on this commonly performed procedure.

An exhaustive search of the literature surrounding surgical technique and outcomes after ray amputation yielded several papers on the benefits of various soft tissue flaps for covering wound defects but just one detailing a particular methods of bone transection. However, Moodley et al focused on the use of a Gigli saw, which is beyond the scope of this feasibility

study(12). There have been no randomised controlled trials evaluating the impact of metatarsal transection method on outcomes after ray amputation, specifically whether a manual bone cutter or an electric/oscillating/pneumatic bone saw were used. We hypothesise that utilising a manual bone cutter is more subject to inter-user variability, as it depends on the physical strength of the operating surgeon; improperly applied forces are liable to fracture the remaining bone, leaving small comminuted fragments that may become necrotic and act as a nidus for further infection within the wound bed. Furthermore, using an oscillating microsaw has the advantage of providing a clean bony transection regardless of the physical strength of the operator, however it may cause more damage to the surrounding connective tissues and disturb microvascular periosteal supply, which could also lead to osteonecrosis. We propose a pilot randomised controlled trial to test the feasibility and to generate sufficient data to permit sample size calculation for a trial designed to evaluate the outcomes after ray amputation using either a bone cutter or a bone saw.

4. **Objectives:**

The principal research question for this trial is as follows:

2.1 Primary Objective

The primary objective of this feasibility study is to collect sufficient data to enable an accurate power calculation for a future randomised controlled trial.

2.2 Secondary Objectives

1. To determine the effect of oscillating microsaw compared to bone cutters for toe amputation on rates of surgical reintervention at six months;
2. To determine the effect of oscillating microsaw compared to bone cutters for toe amputation on re-infection rates;
3. To determine the effect of oscillating microsaw compared to bone cutters for toe amputation on time to surgical wound healing;

4. To determine the effect of oscillating microsaw compared to bone cutters for toe amputation on wound-related hospital readmissions at six months;
5. To determine the effect of oscillating microsaw compared to bone cutters for toe amputation on ulcer healing;
6. To determine the effect of oscillating microsaw compared to bone cutters for toe amputation on ulcer recurrence;
7. To determine the effect of oscillating microsaw compared to bone cutters for toe amputation on osteomyelitis recurrence in the affected foot;
8. To determine the effect of oscillating microsaw compared to bone cutters for toe amputation on resection specimen margin culture positivity;
9. To determine the effect of oscillating microsaw compared to bone cutters for toe amputation on patient-reported post-operative pain, as measured by the Verbal Rating Scale (VRS)(13, 14);
10. To determine the effect of oscillating microsaw compared to bone cutters for toe amputation on patient-reported health-related quality of life (HR-QoL) at 6 weeks and 6 months post-operatively, as measured by the EQ-5D-5L tool(15)

3. Study Design and Endpoints:

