3.2.2 Primary Safety Endpoint

The primary safety endpoint is the rate of vascular-related post-operative complications in each group.

4. Study Participants:

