7.4 Event Reporting

All adverse events will be reported directly to the either the site or principal investigator. Recurrent adverse events or serious adverse events in isolation will be reported in turn to the local Ethical Committee and the risk assessment department for risk analysis.

8. Statistical considerations:

Post intervention, all patient outcomes will be recorded and assessed on intention to treat basis. We expect a certain degree of crossover from the bone cutter trial arm to bone saw trial arm, as is reflected in daily surgical practice. Furthermore, we expect a small number of patients may ultimately not undergo treatment as initially planned. Any losses to follow up will be reported. There are no studies investigating this particular trial question, as such there is no data on which to base a power calculation. For this pilot trial, we aim to recruit 20 patients into each arm i.e. 40 patients in total. All analyses will be performed on an intention to treat basis. The statistical analysis will be blinded. Binary outcomes will be analysed using the Chi-Square test. Non-parametric continuous variables will be compared using Mann-Whitney U Test. The time between surgery and measurable endpoints will be compared using Kaplan-Meier Survival Curves.

9. Ethical Considerations:

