9.2 Data Protection

All data shall be managed in the strictest confidence by approved trial investigators in accordance with Irish data-protection law. Datasets will be anonymous, encrypted and stored in a secure centralised sever (REDCap).

10. Discussion:

At present, ray amputation can be performed using a bone cutters or a bone saw to transect the metatarsal shaft, depending on institutional availability and surgeon preference. There is a dearth of published literature comparing outcomes achieved between the two techniques.

Certainly, there has been no randomised controlled trials published. This randomised controlled feasibility study aims to provisionally compare the value and safety profile of two different surgical techniques. An initial feasibility study was selected as a significant number of patients are needed to power a full study. We plan to recruit from multiple sites after the initial cohort has been selected.

References:

2. Emerging Risk Factors C, Sarwar N, Gao P, Seshasai SR, Gobin R, Kaptoge S, et al. Diabetes mellitus, fasting blood glucose concentration, and risk of vascular disease: a collaborative meta-analysis of 102 prospective studies. *Lancet*. 2010;375(9733):2215-22.

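### Section 2.2 sets ten effect-determining secondary objectives, and Section 8 answers them with unadjusted between-arm tests in an unpowered 40-patient pilot, where estimates with confidence intervals, labelled exploratory, would serve better

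*Combined protocol and SAP*

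**What the plan says.** Section 2.2 numbers ten secondary objectives with a common opening. The first is "To determine the effect of oscillating microsaw compared to bone cutters for toe amputation on rates of surgical reintervention at six months" and the second is "To determine the effect of oscillating microsaw compared to bone cutters for toe amputation on re-infection rates". The tenth, on quality of life, is assessed "at 6 weeks and 6 months post-operatively, as measured by the EQ-5D-5L tool".

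Section 8 covers the analysis in a few sentences. "Binary outcomes will be analysed using the Chi-Square test". "Non-parametric continuous variables will be compared using Mann-Whitney U Test". Times from surgery are to be compared by Kaplan-Meier curves, with no test named. The target is 20 patients per arm, 40 in total, and the section says that no data exist on which to base a power calculation.

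Section 3.2 adds a primary efficacy endpoint (surgical reintervention at twelve months) and a safety endpoint: "The primary safety endpoint is the rate of vascular-related post-operative complications in each group". Section 2.1, in contrast, makes the primary objective the collection of data for a future power calculation. The Discussion (Section 10) says: "This randomised controlled feasibility study aims to provisionally compare the value and safety profile of two different surgical techniques".

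The plan states no significance level, multiplicity rule, order of testing, exploratory status or confidence intervals.

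**The concern.** Followed as written, Section 8 yields about ten unadjusted p-values, and Section 2.2 presents each one as an answer about the tool. With that many tests, a small p-value somewhere is quite likely even if saw and cutter perform identically. It could then be reported as an effect of one tool.

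The tests also do little for the stated purpose. A power calculation needs event rates, spread, retention and a measure of how uncertain they are. A p-value supplies none of these. At 20 per arm, only a large observed gap can reach significance, so a result singled out because it was significant would tend to overstate the difference. If such a result informed the next trial's assumptions, that trial could be too small.

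**Working it through.** **Stated figure.** The plan has no error-rate or power calculation to reproduce. Its only figure is the sample size, and 2 × 20 = 40 is consistent.

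**Inputs from the plan.**
- Ten secondary objectives. Seven are naturally binary: reintervention, re-infection, readmission, ulcer healing, ulcer recurrence, osteomyelitis recurrence and margin culture. Three are not: healing time, pain and EQ-5D-5L.
- EQ-5D-5L has two time points, so testing each gives 11 comparisons.
- 20 patients per arm.

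**Assumptions, because the plan is silent.** Two-sided 5% per test; correlation between outcomes varied; Chi-Square taken with and without continuity correction; healing time counted as one test.

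**Step 1: independent tests.** The chance of at least one false positive is 1 − 0.95^m.
- m = 10: 1 − 0.95^10 = 40.1%
- m = 11: 1 − 0.95^11 = 43.1%
- m = 9 (EQ-5D-5L counted once, no test on healing time): 1 − 0.95^9 = 37.0%
- m = 13 (11 plus the efficacy and safety endpoints): 1 − 0.95^13 = 48.7%

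The expected number of false positives is 10 × 0.05 = 0.5, or 11 × 0.05 = 0.55, whatever the correlation.

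**Step 2: correlated tests.** Test statistics were simulated as Z_j = √ρ·U + √(1−ρ)·e_j, with U and e_j standard normal. The result is the share of 200,000 draws in which any |Z_j| exceeds 1.96.

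| ρ | m = 10 | m = 11 |
|---|---|---|
| 0.3 | 35.2% | 37.5% |
| 0.5 | 28.7% | 30.4% |
| 0.7 | 21.4% | 22.3% |
| 0.9 | 12.9% | 13.2% |

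**Step 3: patient-level simulation.** Null trials of 20 v 20 had seven binary outcomes and three or four rank-tested ones. Event rates were 14.4% throughout, 43% throughout (both figures from the Irish series cited in the background), or a mix of 20-43%. Latent correlation ran from 0 to 0.7.

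| Chi-Square version | 10 outcomes | 11 outcomes |
|---|---|---|
| Uncorrected | 26-40% | 27-43% |
| Continuity-corrected | 16-25% | 17-29% |

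The correction matters because it lowers the exact size of one 20 v 20 test to about 1-2% at event rates of 14.4-50%. The uncorrected size there is about 4-5%. At a 5% event rate even the uncorrected test rejects only 1.2% of the time.

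**Step 4: the gap needed for significance.** For 4/20 v 10/20, the uncorrected statistic is 40 × (4×10 − 10×16)² / (20×20×14×26) = 576,000 / 145,600 = 3.96, p = 0.047. With continuity correction the numerator is 40 × (120 − 20)² = 400,000, giving 2.75, p = 0.097. For 4/20 v 9/20, the uncorrected statistic is 40 × (4×11 − 9×16)² / (20×20×13×27) = 400,000 / 140,400 = 2.85, not significant at 5%. So a 30-point gap is borderline, and it passes only without the correction.

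**Step 5: what an interval would show.** If both arms had a 43% event rate (an assumption taken from the cited series), the standard error of the difference is √(2 × 0.43 × 0.57 / 20) = 0.157. The 95% half-width is 1.96 × 0.157 = 0.31, or about 31 percentage points. An interval shows this uncertainty directly; a p-value does not.

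**The case against.** The strongest reply is that nobody should mistake this for a confirmatory trial. The background presents it as a pilot to test feasibility and inform a sample size, and leaves evaluation of outcomes to a later trial. Section 2.1 makes that the primary objective, Section 3.1 calls the design a feasibility study, Section 8 calls it a pilot and admits that it has no basis for power, and the Discussion says many more patients are needed for a full study. Pilots are often left unadjusted, and these outcomes already rank below named primary endpoints. This largely stands, and a reader who inferred that one word in the Discussion is the plan's only caution would be wrong. But none of this framing says how the ten comparisons are to be analysed or interpreted, and Sections 2.2 and 8 point the other way.

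Three further limits stand.
- **The count is uncertain.** Kaplan-Meier names no test, so healing time may yield no p-value, and separate EQ-5D-5L tests are inferred. On the other side, re-infection and pain have no stated time point, so the count could also rise.
- **The version of Chi-Square is not given**, and it changes the result materially.
- **The 5% level is an assumption.** The plan promises no error rate, so none is breached.

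A reader might also infer that the sponsor intends to claim superiority or to choose the main trial's endpoint by p-value. No section says so; these are risks that the wording leaves open.

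**Conclusion.** The concern holds as a matter of analysis and interpretation: effect-determining objectives, unadjusted between-arm tests, no power calculation, and nothing in Section 8 that limits what the results may be taken to show.

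No single false-positive figure can be drawn from the documents. A reader might settle on 30%, but that needs 11 comparisons, a 5% level and a correlation of 0.5, none of which the plan states. The supportable statement is a range, with 5% assumed per test: about 40-43% for 10-11 independent tests, about 29-30% at correlation 0.5, and about 16-25% for ten outcomes (up to 29% for eleven) with a continuity-corrected Chi-Square. Very high correlation lowers it further, to about 13% at 0.9 with nominal 5% tests, and rare events would lower it too. All the scenarios run for the whole set of comparisons stay well above 5%.

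Nor do the documents support saying that any significant secondary result must be exaggerated. That depends on the true effect; the supportable point is that selecting on significance at this sample size tends to overstate it.

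This is a cheap improvement to the plan. It does not invalidate the pilot.

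**What to change.** **Section 2.2.** Change the opening of each objective from determining an effect to estimating it, for example: *To estimate, as an exploratory comparison, the effect of …*

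**Section 8.** Replace the testing sentences with text along these lines: *All between-arm comparisons, including reintervention at twelve months and the safety endpoint, are exploratory. They are reported as differences (or median differences) with 95% confidence intervals in place of significance tests. No conclusion of superiority or safety of either tool, and no choice of the main trial's endpoint, will rest on a p-value from this pilot.*

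The twelve-month endpoint should not be exempted: it rests on the same 40 patients and is equally unpowered. Kaplan-Meier curves can stay as a descriptive display.

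**Cost.** Wording in two sections, with no change to patients, visits or data. The sponsor gives up any claim of a significant result from the pilot.

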4.5 Baseline patient data

Patients will have a full medical history taken and clinical examination as part of their standard care. The following will be recorded:

1. Weight;
2. Height;
3. Blood pressure;
4. Heart rate;
5. ECG findings;
6. Gender;

7. Ethnicity;
8. Date of birth;
9. Diabetes mellitus and glycaemic control, defined as the most recent HbA1c;
10. Insulin requirement for diabetic patients;
11. Hypercholesterolaemia;
12. Hypertension;
13. Previous myocardial infarction;
14. Previous coronary revascularisation;
15. Previous stroke;
16. Atrial fibrillation;
17. Peripheral arterial disease;
18. Smoking history;
19. Recent ipsilateral lower limb re-vascularisation;
20. ABPI +/- TPI in the index limb;
21. Chronic kidney disease, as defined by eGFR;
22. Baseline bloods at hospital admission, including white cell count, neutrophil count, haemoglobin, mean corpuscle volume, CRP, creatinine and urea, albumin, total protein
23. Baseline x-ray findings, including degree of osteomyelitis, osteopenia and soft tissue gas

5. Interventions

All procedures will be carried out by a vascular consultant or trainee with significant experience in the procedure. This will be a transmetatarsal amputation performed using either a bone cutter or a bone saw. The aim is for a successful healing of the wound, and no further re-interventions or re admission within a year. All patients will receive saline wound lavage. Wounds with extensive contamination will receive washout with 50% hydrogen peroxide solution. The most proximal specimen of bony resection will be sent for culture and sensitivity to the microbiology laboratory. The use of a drain and closure material are left to the discretion of the operating surgeon.

Continuation of antibiotics will be as per local microbiology guidelines and cultures and sensitivities will be followed. Patients will be followed up with x-ray within 48 hours of surgery to assess for bony fragments. Use of VAC or wound adjuncts will be documented.

6. Schedule of Events:

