6.4 Protocol Violations

The following will be deemed a protocol violation and the participant will be removed from the trial:

1. Non-adherence to repeat imaging;
2. Withdrawal of consent for procedure or inclusion in study.

	Screening	Enrolment	Intervention	Follow up 6 weeks	Follow op 6 months	Follow up 1 year
Consent		X				
History and Exam	x	X				
Imaging	x		x		x	x
Intervention			x	x	x	x
Clinical follow-up				x	x	x

7. Safety Parameters:

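### EQ-5D-5L is compared at 6 weeks and 6 months with no baseline score collected, which gives up precision that one short questionnaire before randomisation could recover

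*Combined protocol and SAP*

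**What the plan says.** Section 2.2, item 10, sets the quality-of-life comparison "at 6 weeks and 6 months post-operatively, as measured by the EQ-5D-5L tool". No pre-operative time is named. Item 9 compares post-operative pain on the Verbal Rating Scale (VRS) and states no assessment time.

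Section 4.5 introduces the baseline data set with "Patients will have a full medical history taken and clinical examination as part of their standard care. The following will be recorded" and then lists 23 items: demographics, comorbidity, limb pressures, bloods and imaging. The last is "Baseline x-ray findings, including degree of osteomyelitis, osteopenia and soft tissue gas". None is a quality-of-life or pain score.

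The schedule table after Section 6.4 has rows for consent, "History and Exam", imaging, intervention and clinical follow-up. It has an enrolment column but no questionnaire row at any visit.

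Section 8 states "Non-parametric continuous variables will be compared using Mann-Whitney U Test". It also names the chi-square test for binary outcomes and Kaplan-Meier curves for times to event. It does not say which method applies to EQ-5D-5L, and it mentions no covariate adjustment. On size, "we aim to recruit 20 patients into each arm i.e. 40 patients in total".

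**The concern.** Patients come from in-patient and out-patient settings, and their operations may be emergent, urgent or elective (Section 3.1), so starting quality of life is likely to vary. Part of the spread in the 6-week and 6-month scores will reflect where each patient began. A baseline score lets the analysis remove that part; without one it stays in the standard error.

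The balancing factors do not do this job. Section 4.1 names pulse status and eGFR, and Section 4.4 seeks balance across sites. Quality of life and urgency are not among them. With only 20 per arm, a gain in precision at almost no cost is worth having. A pre-operative score also cannot be collected once the operation is done, so the loss is permanent for each patient treated.

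**Working it through.** **The plan's own figure.** 2 × 20 = 40, as Section 8 states. Section 8 says there are no data for a power calculation, so there is nothing else to reproduce.

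**Inputs.** From the documents: n = 20 per arm and 1:1 allocation. Assumed, because the documents give no value: baseline-to-follow-up correlation r of 0.2 to 0.7, no dropout (so the precision shown is a best case), and a linear model with results in outcome-SD units.

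**Step 1: unadjusted precision.** SE of the difference in means = √(2/20) = 0.316 SD. The 95% half-width is 1.96 × 0.316 = 0.62 SD.

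**Step 2: baseline adjustment.** Residual variance under ANCOVA is (1 − r²) of the unadjusted variance. Estimating the slope multiplies this by about 1 + 1/(2n − 4) = 1 + 1/36 = 1.028. The equivalent unadjusted n per arm is 20 divided by the net factor.

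| r | 1 − r² | Cut before slope cost | Net factor (× 1.028) | Net cut | Equivalent n per arm | 95% half-width before slope cost (SD) |
|---|---|---|---|---|---|---|
| 0.2 | 0.96 | 4% | 0.987 | about 1% | 20.3 | 0.61 |
| 0.3 | 0.91 | 9% | 0.935 | about 6% | 21.4 | 0.59 |
| 0.5 | 0.75 | 25% | 0.771 | about 23% | 25.9 | 0.54 |
| 0.7 | 0.51 | 49% | 0.524 | about 48% | 38.2 | 0.44 |

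**Step 3: change scores are no substitute.** The variance of a change score, relative to the raw follow-up score, is 2(1 − r). That is 1.4 at r = 0.3, 1.0 at r = 0.5 and 0.6 at r = 0.7. It is worse than no adjustment at 0.3, no better at 0.5, and less efficient than ANCOVA (0.51 before the slope cost) at 0.7.

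**Step 4: what chance imbalance does.** Under simple randomisation, a baseline difference has an SD of 0.316 SD units, so it exceeds 0.3 SD in 2 × [1 − Φ(0.3/0.316)] = 34% of trials. Only r times that difference reaches the follow-up contrast: 0.3 × 0.3 = 0.09 SD up to 0.7 × 0.3 = 0.21 SD. This variation is already inside the standard error of Step 1. It is the same loss seen from another side, not an additional one.

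**The case against.** The strongest reply is that a follow-up-only randomised comparison is sound, and that this concerns minor objectives of a 40-patient pilot. Both parts stand. A reader might infer several stronger claims, which the documents do not support:

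- **That the comparison is biased or invalid.** Randomisation keeps it unbiased on average, and its standard error already allows for chance imbalance. The 34% in Step 4 describes the baseline score, not an error in the result. It also assumes simple randomisation; minimisation on pulse status and eGFR could lower it if those factors relate to quality of life.
- **That imbalance cannot be corrected at all.** Section 4.5 records HbA1c, peripheral arterial disease, CRP, albumin and other covariates that could adjust in part. What is missing is the outcome's own baseline and any planned adjustment.
- **That the main trial needs this correlation for its sample size.** The only stated primary efficacy endpoint is binary, surgical reintervention at twelve months (Section 3.2.1), and sizing on it needs event rates. Nothing says a later trial will be powered on EQ-5D-5L.
- **That pain is an equal case.** The VRS is ordinal, its assessment time is not stated, and pre-operative pain may predict post-operative pain only weakly.

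It can also be said that the schedule's silence proves little, because it has no questionnaire row even at 6 weeks and 6 months, when EQ-5D-5L is planned. That is fair for the table alone. But item 10 and the itemised list in Section 4.5 also provide no baseline, and Section 8 plans no use of one.

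**Conclusion.** The point holds as a loss of precision on one secondary outcome. With no baseline EQ-5D-5L and no adjusted analysis, the pilot forgoes a net variance reduction of about 6%, 23% or 48% at an assumed r of 0.3, 0.5 or 0.7, and about 1% at 0.2. The benefit therefore runs from negligible to large, and the documents do not show where in that range it falls. The figures assume a linear analysis and complete follow-up. The change is worth making because it is cheap and the score cannot be recovered later, not because the planned comparison is wrong. The reintervention endpoint is not affected.

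**What to change.** 1. Add EQ-5D-5L to the Section 4.5 list and to the enrolment column of the schedule table, completed after consent and before randomisation. Section 4.4 places randomisation on the day of surgery, so there is room for it. Show the 6-week and 6-month questionnaires in the same new row.
2. In Section 8, state that the 6-week and 6-month EQ-5D-5L scores are each analysed by ANCOVA on the baseline score. Collecting the baseline alone is not enough, because an unadjusted Mann-Whitney test would ignore it.
3. Report the baseline-to-follow-up correlation at each time, for use if the main trial keeps EQ-5D-5L as an outcome.
4. A pre-operative VRS is optional. If it is added, state the post-operative assessment time and choose a baseline-adjusted method suited to an ordinal scale.

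The cost is one short questionnaire per patient. Baselines from acutely unwell patients may correlate less with follow-up, which would shrink the gain; because they are taken before allocation, they would not bias the comparison.
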